## STUDY SUMMARY

Title	Pravastatin Intervention to Delay Hepatocellular Carcinoma Recurrence
Protocol Number	IIT2017-[name]-StatLv
Phase	Phase II
Methodology	Randomized, double-blinded, placebo-controlled, Phase II trial of statin to increase time to recurrence in patients with liver cirrhosis and initial hepatocellular carcinoma
Study Duration	5 years
Study Center(s)	Cedars-Sinai Medical Center (CSMC), Ronald Reagan UCLA Medical Center (UCLA), Northwestern Memorial Hospital (NWU), UCSF Medical Center (UCSF), Emory University Woodruff Health Sciences Center (EU)
	Primary Objective: To evaluate the effect of a pravastatin intervention versus placebo on the change in time to recurrence (TTR) from baseline to 12 months following treatment initiation.
Objectives	
 
Secondary Objective: To evaluate the effect of a pravastatin intervention versus placebo at 12 months from baseline on:
 
1) Recurrence-free survival
 
2) Overall survival
 
3) Waitlist drop-off
 
4) Change in liver stiffness
 
5) Change in liver fat fraction
 
6) Change in serum biomarkers of monocyte/macrophage and stellate cell activation
 
7) Levels of liver tissue markers related to HCC
 

Number of Subjects	130
Diagnosis and Main Inclusion Criteria	Patients with a confirmed diagnosis of liver cirrhosis (Child-Pugh A or B); current Model for End-Stage Liver Disease (MELD) < 30; Minimum 18 years of age; HCCs must fall within the Milan Criteria or OPTN tumor downstaging criteria; receipt of LRT with verification of adequate response; and patients whose lab results meet the inclusion criteria after the Screening visit blood tests.
Study Product(s), Dose, Route, Regimen	Pravastatin 40 mg and placebo identical in color, consistency, and appearance to pravastatin; oral administration daily (N=65 in each group)
Duration of administration	12 months
Statistical Methodology	Statistical analyses for the primary objective will be conducted on participants who complete the 12 month MRI or CT and blood specimen collection. The distribution of the clinical and demographical covariates, including but not limited to; age, race, smoking status, BMI, and comorbid conditions, will be summarized and compared between the intervention and control groups to assess the adequacy of the randomization. Chance differences between groups will be adjusted for using multiple regression modeling.

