#### Criteria fulfillment will be confirmed by the *Imaging Charter* and MedQIA.

- **4.1.4** Initiation of LRT (according to clinical judgement) within 24 months prior to Screening Visit, with adequate response as determined by *Imaging Charter* and MedQIA.
- **4.1.5** ECOG performance status  $\leq$  1 (or Karnofsky  $\geq$  70%; see Appendix A)
- **4.1.6** AST (SGOT) & ALT (SGPT) ≤ 5x institutional ULN
- **4.1.7** AFP < 400 ng/mL
- **4.1.8** Ability to understand and the willingness to sign a written informed consent document and medical release
- **4.1.9** Agree to use adequate contraception (hormonal or barrier method of birth control; abstinence) prior to study entry and for the duration of study participation; for women who are able to become pregnant.
- **4.1.10** Willing and able to comply with trial protocol and follow-up

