## 9.3.1 Analysis of Primary Endpoint: TTR

The log-rank test will be carried out to compare the distributions of TTR between placebo and pravastatin groups and the Kaplan-Meier estimators will be presented graphically. Cox proportional hazards model will be fitted to the data where the explanatory variable of interest is the indicator of treatment allocation adjusting for clinical and demographic baseline covariates, including sex. Patients who did not experience HCC recurrence, or receive a liver transplant and are still alive at the end of the study will be right censored. Patients who are transplanted or die before HCC recurrence will be treated as a competing risk. A competing risk model for TTR will be used to estimate the cumulative incidence of TTR using time to transplant or death as a competing risk. The proportional hazards assumption will be tested graphically and analytically, and model diagnostics such as martingale and Schoenfeld residuals will be conducted to assess model adequacy. Violation of the proportional hazards assumption will be addressed by use of time-dependent covariates or extended Cox models. The possibility of collinearity among the explanatory variables will be reduced after careful assessment of the correlation matrix and condition index. Automatic variable selection methods in a multivariable Cox proportional hazards model such as stepwise, backward, and forward will be used as a guideline to identify sets of important predictors and a more rigorous approach based on a 4-step procedure outlined in Collett (2003) will be employed (55). Power. Preliminary data indicate that the 12-month RFS is between 57% and 78% in patients with: 1) Child Pugh A or B cirrhosis, 2) small HCCs (typically meeting Milan criteria) 3) liver directed therapy (typically RFA or resection), and 4) no other interventions (27, 56-59). Therefore, we will assume that the 12-month RFS in the control group is 65%. Assuming a common cumulative incidence of the competing risk events at 12 months of 20% (10% due to liver transplant and 10% due to death), a 42-month accrual time and 15-month follow up time, and 10% drop out, data from 47 patients per group achieve 80% power to detect a hazard ratio of 0.45 using a two-sided log-rank test with a 0.1 level of significance. This is equivalent to detecting a decrease in the 12-month cumulative incidence of disease recurrence from 35% in the control group to 18% in the treatment group, which is clinically meaningful. The choice of a type I error rate of 0.1 is appropriate for a randomized phase II trial since this can serve as a randomized screening design for a nondefinitive comparison of statin vs placebo (reference: Mandrekar and Sargent (2010)). We further assumed that TTR and time to death or transplant are independent and exponentially distributed. Statistical power was based on the formulas in Machin et al. (2008) and Pintilie (2006) and were carried out using PASS version 13 (60, 61).

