Liver stiffness and Liver fat fraction. The two-sample t-test will be used to compare the change in liver stiffness/fat fraction from 3 to 12 months between pravastatin and placebo groups. If the distribution of the change in liver stiffness/fat fraction is highly skewed so that the sample mean based on 47 measurements is not approximately normally distributed, the Mann-Whitney test will be used instead. Measurements of liver stiffness vary between 1.5 and 75 kPa. Therefore, we conservatively estimate the standard deviation of liver stiffness at 3 months as (75-1.5)/4 = 18.4. If X and Y denote the random variables of liver stiffness at 3 and 12 months, respectively, the Var(Y-X) = Var(X)+Var(Y)-2p Var(X) Var(Y), where p is the correlation coefficient between X and Y. Assuming a non-negative correlation between the measurements at 3 and 12 months and the same variance at 12 months  $\sigma$ 2, then a conservative estimate for the standard deviation of the change in liver stiffness is 1.4  $\sigma$ . Therefore, data from 47 patients per group achieve 80% power to detect an effect size of 0.5 using a two-sided two-sample t-test with 0.1 level of significance. We therefore have enough patients to detect clinically meaningful differences in mean liver stiffness. Here, the effect size is the ratio of the difference in the mean change between the two groups relative to the baseline standard deviation  $\sigma$ assumed to be the same for the treatment and control groups. Linear regression analysis will be carried out to estimate the adjusted pravastatin effect if there is evidence of imbalance between the two groups with respect to one or more baseline clinical and demographic covariates.

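### The adjusted Cox estimate of the pravastatin effect is built by automatic selection from an open covariate list; with about 25–40 events this can raise its type I error from 0.10 to roughly 0.11–0.16

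*Combined protocol and SAP*

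**What the plan says.** Section 9.3.1 first compares TTR by a log-rank test. The power statement (80%, hazard ratio 0.45, 47 per arm) and the error rate belong to that test: "using a two-sided log-rank test with a 0.1 level of significance".

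It then fits a Cox model in which treatment is the variable of interest, adjusted for baseline covariates of which only sex is named. To choose covariates, "Automatic variable selection methods in a multivariable Cox proportional hazards model such as stepwise, backward, and forward" serve as a guideline, alongside a four-step procedure from a cited source that is described as more rigorous. There is no closed candidate list, no entry or exit threshold, and no statement of whether treatment is in the model while covariates are selected.

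The Study Summary (Statistical Methodology) gives five examples of covariates (age, race, smoking status, BMI, comorbid conditions) and leaves the list open. Section 9.1 blocks the randomisation by site and initial HCC treatment type, but neither is named as a model term. Section 9.3.2 compares RFS and OS by the same Cox model and names no log-rank test for them.

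A second route to adjustment appears elsewhere. The Study Summary says "Chance differences between groups will be adjusted for using multiple regression modeling". Section 9.3.2 adds a regression for liver stiffness and fat fraction "if there is evidence of imbalance between the two groups with respect to one or more baseline clinical and demographic covariates", with similar wording for the biomarkers. Evidence of imbalance is not defined.

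**The concern.** A log-rank test yields no hazard ratio, so the hazard ratio and interval that readers quote will come from the Cox model. If the outcome data choose its covariates while treatment is in the model, the usual standard error takes no account of that choice. The p-value is then too small and the interval too narrow. Forward, backward and stepwise routes can also give different answers from the same data. The problem grows as events become few relative to candidates. For RFS and OS this Cox model is the only comparison that section 9.3.2 names.

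**Working it through.** **1. The plan's power figure.** Inputs from section 9.3.1: 35% recurrence in controls ("decrease in the 12-month cumulative incidence of disease recurrence from 35% in the control group to 18% in the treatment group"), competing events ("cumulative incidence of the competing risk events at 12 months of 20" percent), hazard ratio 0.45, two-sided alpha 0.10, 47 per arm, 42-month accrual, 15-month follow-up and 10% drop-out (taken here as 10% per year). Under exponential cause-specific hazards:

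- Total hazard = −ln(1 − 0.35 − 0.20) = 0.7985 per year. Recurrence = 0.7985 × 0.35/0.55 = 0.508; competing = 0.7985 × 0.20/0.55 = 0.290.
- On pravastatin, recurrence hazard = 0.45 × 0.508 = 0.229. Twelve-month incidence = (0.229/0.519) × (1 − e^−0.519) = 17.8%, matching the stated 18%.
- Events required (Schoenfeld) = 4 × (1.645 + 0.842)² / (ln 0.45)² = 38.8, so 39. The Freedman formula gives 43.
- Expected events with uniform accrual = 37.8. Power = Φ(√37.8 × 0.7985/2 − 1.645) = 0.79. The stated 80% is reproduced.

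**2. Events inside the TTR window.** Section 2.3 counts TTR events only within 12 months. Without drop-out, events at hazard ratio 0.45 are 47 × (0.35 + 0.178) = 24.8 for the 94 patients in the analytic sample (section 9.2), or 65 × (0.35 + 0.178) = 34.3 for all 130. With 10% per year drop-out they are 23.7 and 32.8. Under no effect they are about 31–33 and 44–46. The adjusted model therefore rests on about 25–40 events.

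**3. Type I error at nominal 0.10.** Simulation with no treatment effect, the rates above, the 12-month window and 3,000 trials per row (Monte Carlo SE about 0.005–0.008). The documents do not give the number or strength of candidates. Assumed: 8 or 15 candidates, of which none or three are prognostic (log hazard ratio 0.5 per SD).

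| n | Candidates (prognostic) | Mean events | Log-rank | 2–3 fixed covariates | Stepwise p<0.10, treatment in | Backward p<0.10, treatment in | Select, then add treatment | Imbalance-triggered only |
|---|---|---|---|---|---|---|---|---|
| 94 | 15 (3) | 27.3 | 0.100 | 0.098 | 0.161 | 0.164 | 0.100 | 0.089 |
| 94 | 8 (3) | 27.2 | 0.098 | 0.101 | 0.128 | 0.130 | 0.100 | 0.082 |
| 94 | 15 (0) | 31.4 | 0.097 | 0.097 | 0.135 | 0.140 | 0.098 | 0.094 |
| 94 | 8 (0) | 31.3 | 0.097 | 0.101 | 0.112 | 0.113 | 0.099 | 0.098 |
| 130 | 15 (3) | 37.7 | 0.110 | 0.108 | 0.143 | 0.147 | 0.112 | 0.094 |
| 130 | 8 (3) | 37.8 | 0.096 | 0.097 | 0.112 | 0.112 | 0.098 | 0.085 |
| 130 | 15 (0) | 43.5 | 0.102 | 0.103 | 0.127 | 0.131 | 0.102 | 0.102 |
| 130 | 8 (0) | 43.4 | 0.098 | 0.094 | 0.105 | 0.106 | 0.097 | 0.093 |

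A looser stepwise threshold (p<0.25) gave 0.113–0.185. Entering every candidate without selection gave 0.114–0.160, so part of the inflation is too many parameters for the events.

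**4. Does a fixed list cure it?** Only if it is short. Five sites need four coefficients, treatment type at least one and three prognostic values three: eight covariate parameters. In further simulations at the same rates and window (2,000–2,500 trials per cell, about 29–40 events), that fixed model still gave 0.108–0.139. Handling site and treatment type as strata gave 0.097–0.109. In the 2,000-trial set, three fixed covariates gave 0.099–0.114 and backward selection with treatment in the model gave 0.129–0.152.

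**The case against.** The strongest reply is that the log-rank test carries the stated alpha and power, and covariate selection cannot touch it. That stands. A reader might infer that the trial's primary false-positive rate is inflated. The documents do not support this, because they never make the adjusted Cox result decisive. They do not rule it out either, and section 9.3.2 names only the Cox model for RFS and OS.

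A second reply is that automatic selection is only a guideline and the four-step procedure governs. This stands in part. The procedure is in an outside source (reference 55, while the printed list ends at 37), so its handling of treatment cannot be seen. If treatment enters last, the inflation is about nil. The plan does not require that order.

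Two further inferences are tempting. One is that imbalance-triggered adjustment also inflates type I error. It does not: the simulated rate was 0.082–0.102. Section 9.3.1 has no such trigger, and for stiffness, fat fraction and biomarkers the named comparison is an unadjusted test. What remains is a model that depends on the data. The other is that the unblinded biostatisticians (sections 5.3 and 10.3.2) would pick covariates knowing the arms. The documents do not say who selects them.

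Finally, section 9.3.1 calls the comparison nondefinitive, and a drift of a few points is modest. That limits the urgency but does not justify leaving the model open.

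**Conclusion.** The concern holds for the adjusted Cox result. If selection is run with treatment in the model, its type I error rises from 0.10 to roughly 0.11–0.16. The worst case is 94 patients with 15 candidates (about 27 events); with 130 patients and eight candidates the excess is about one point or less. These figures rest on assumed candidate numbers, strengths and thresholds. The plan names six covariates, counting sex, but leaves the list open, and several of them can take more than one parameter. The simulations concern TTR; the size for RFS and OS was not computed.

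**What to change.** - Name the log-rank test, stratified by the randomisation factors, as the decisive TTR test.
- For the adjusted hazard ratio (TTR, RFS and OS), replace automatic selection with a Cox model stratified by those factors, not one with a coefficient per site.
- Use initial treatment type alone as the stratum if site strata are too sparse. With two treatment categories (assumed), five sites give ten strata and about 24.8/10 = 2.5 to 34.3/10 = 3.4 events each at hazard ratio 0.45.
- Add no more than two or three prognostic covariates already collected, fixed before unblinding and used whatever the observed balance. Examples are AFP, tumour burden before LRT, and time from LRT to randomisation, which can vary widely given "Initiation of LRT (according to clinical judgement) within 24 months prior to Screening Visit" (section 4.1.4).
- Remove the imbalance trigger from treatment-effect models, and keep variable selection only for a separately labelled exploratory analysis of predictors.

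The cost is SAP wording. The covariates must be named before data are seen, and small strata lose a little information.

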#### • Secondary Efficacy Endpoints

Secondary endpoints include recurrence-free survival (RFS), overall survival (OS), waitlist survival, liver stiffness, liver fat fraction, circulating biomarkers, and liver tissue biomarkers. Differences in secondary endpoints will be compared in the pravastatin and placebo groups.

1) RFS: We will assess the effect of pravastatin on RFS. RFS will be defined as the time from randomization to the first occurrence of a documented HCC recurrence, within the 12-month intervention and assessment period.

2) OS: We will examine the effect of pravastatin on OS (defined as the time from randomization to death from any cause).

3) Waitlist drop-off: We will evaluate the effect of pravastatin on reducing waitlist dropout due to any of the following causes: 1) HCC progression outside of Milan/T2 criteria, 2) cirrhosis progression (too sick to transplant), or 3) death.

Participants who are delisted for other reasons (such as positive alcohol test) will be censored at date of delisting.

4) Change in liver stiffness: We will evaluate the effect of pravastatin on withinperson change in liver stiffness, as measured by magnetic resonance elastography (MRE) or FibroScan, between Study Visit 1 (0 month) and Visit 6 (12 month). Within-patient consistency is required between Study Visits 1 and 6 with regards to liver stiffness testing modality (MRE or FibroScan).

5) Change in liver fat fraction: We will evaluate the effect of pravastatin on withinperson change in liver fat fraction, as measured by MRI-proton density fat fraction (PDFF), between Study Visit 1 (0 month) and Visit 6 (12 month).

6) Change in serum biomarkers of monocyte/macrophage and stellate cell activation: We will examine the effect of pravastatin on change in serum biomarkers including cytokines, chemokines, soluble receptors, and proteins (specifically, IL6, TNF $\alpha$ , sTNFRII, IL18BP, sCD163, IL10, IL17, IL-8, CCL17, TGF $\beta$ ).

7) Levels of liver tissue markers related to HCC: We will examine the effect of pravastatin on levels of liver tissue markers related to HCC including those in the Wnt/ $\beta$ -catenin pathway (specifically,  $\beta$ -catenin and glutamine synthetase).

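### The power calculation uses 1 − RFS as the cumulative incidence of recurrence and adds deaths as competing events; unless the cited RFS excluded deaths in a particular way, the stated 80% power may be 1 to about 12 points too high

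*Combined protocol and SAP*

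**What the plan says.** The power paragraph of section 9.3.1 starts from external series: "Preliminary data indicate that the 12-month RFS is between 57% and 78"%. It fixes the control value: "Therefore, we will assume that the 12-month RFS in the control group is 65"%. It then assumes a "common cumulative incidence of the competing risk events at 12 months of 20% (10% due to liver transplant and 10% due to death") and "a 42-month accrual time and 15-month follow up time, and 10% drop out". On these inputs, "data from 47 patients per group achieve 80% power to detect a hazard ratio of 0.45". The comparison is by log-rank test, two-sided at the 0.1 level. The effect is also expressed as a "decrease in the 12-month cumulative incidence of disease recurrence from 35% in the control group to 18% in the treatment group". Recurrence and the competing events are taken as independent and exponential.

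The definition of RFS appears in section 2.3 (Secondary Efficacy Endpoints): "RFS will be defined as the time from randomization to the first occurrence of a documented HCC recurrence". Death is not listed as an event there. Section 9.3.2, on RFS and OS together, lets only transplant compete, which implies that death is an event; the reason it gives concerns OS.

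**The concern.** The 35% is the complement of an RFS figure, but it is used as a cumulative incidence of recurrence alone, beside 10% deaths and 10% transplants. Whether that is coherent depends on what the cited RFS counted.

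- If RFS counts death, 35% recurrence plus 10% death implies an RFS of 1 − 0.35 − 0.10 = 55%. That contradicts the assumed 65% and lies below the plan's own 57–78% range.
- If RFS is recurrence-only and the 65% is a Kaplan-Meier figure with other events censored, 35% is a net risk. The cumulative incidence in the presence of competing events is then lower.
- If the cited figure was one minus a recurrence-only cumulative incidence, 35% stands.

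Recurrences drive the log-rank test, and the plan's inputs yield slightly fewer events than 80% power needs, so a lower control incidence feeds straight into the power. A null result would also be read against 80% power and a 35%-to-18% benchmark.

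**Working it through.** **Inputs (section 9.3.1).** 47 per arm; HR 0.45; two-sided α = 0.1; accrual R = 42 months = 3.5 years; follow-up F = 15 months = 1.25 years; competing cumulative incidence 20% at 12 months. The 10% drop-out is treated here as a yearly loss hazard of −ln(0.9) = 0.105.

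**Formulas.** Let λ1 be the yearly hazard of recurrence, λ2 that of competing events, and L = λ1 + λ2 + 0.105.

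- Cumulative incidences a (recurrence) and b (competing) at 12 months give λ1 = a/(a+b) × [−ln(1−a−b)]; λ2 follows likewise.
- Event probability per patient = (λ1/L) × [1 − (e^(−LF) − e^(−L(R+F)))/(LR)]. The pravastatin arm uses 0.45 × λ1.
- Power = Φ(|ln 0.45| × √D/2 − 1.645), with D the total events.
- Events needed for 80% = 4(1.645 + 0.842)²/(ln 0.45)² = 38.8.

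**The plan's own figure.** With a = 0.35 and b = 0.20, −ln(0.45) = 0.799, so λ1 = 0.508 and λ2 = 0.290. Event probabilities are 0.507 and 0.298, so D = 47 × 0.805 = 37.8 and power = Φ(0.811) = 0.791. The stated 80% is reproduced to about a point. The benchmark also agrees with HR 0.45: the model gives 35.0% against 17.8%.

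**Alternative readings of the 65%.**

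1. Recurrence-only Kaplan-Meier: λ1 = −ln 0.65 = 0.431. If the 20% is a cumulative incidence, as section 9.3.1 words it, λ2 solves to 0.279. If it is treated as a net risk, λ2 = −ln 0.8 = 0.223.
2. RFS counts deaths, by subtraction: a = 0.35 − 0.10 = 0.25, so λ1 = 0.332 and λ2 = 0.266.
3. RFS counts deaths, as a composite Kaplan-Meier with transplant censored: λ1 + λ2/2 = 0.431 with competing incidence 20%, so λ1 = 0.300 and λ2 = 0.261.

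| Reading of the 65% | 12-month recurrence, control vs pravastatin | Events | Power |
|---|---|---|---|
| As used in the plan | 35.0% vs 17.8% | 37.8 | 0.791 |
| Recurrence-only KM, 20% as net risk | 31.6% vs 15.9% | 36.3 | 0.777 |
| Recurrence-only KM, 20% as cumulative incidence | 30.8% vs 15.4% | 34.3 | 0.756 |
| Counts deaths, subtraction | 25.0% vs 12.2% | 29.0 | 0.694 |
| Counts deaths, composite KM | 23.0% vs 11.1% | 27.1 | 0.667 |

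Applying the 10% drop-out as a factor of 0.9 on events gives 0.70 instead of 0.694 in the subtraction row.

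**Sensitivity to the source cohorts' deaths.** The last two rows assume 10% recurrence-free deaths in those cohorts. With 3% or 5%, subtraction gives recurrence of 32% or 30% and power of 0.77 or 0.75.

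**Two features of the stated calculation that also move the figure.**

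- Sample size: 65 × 0.8 × 0.9 = 46.8. So 47 per arm appears to be net of 20% competing events and 10% drop-out already, yet both are applied again in the power formula. On 65 per arm, with the same follow-up and drop-out, the deaths-counted readings give 0.79–0.81.
- Follow-up: section 2.3 ends TTR at 12 months, but the calculation runs over 42+15 months. With 12 months per patient and the plan's 35%/18%, D = 0.9 × 47 × (0.350 + 0.178) = 22.3 and power is about 0.60.

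**The case against.** The strongest reply is that no error has been shown. The stated 80% reproduces, 35% to 18% matches HR 0.45, and the only explicit definition of RFS, in section 2.3, is recurrence-only. On that reading the loss is 1 to 4 points, small for a screening design at α = 0.1; with no further drop-out deducted from 47, power is 0.795 to 0.816. The 67–70% figures need the source cohorts to have had the trial's assumed 10% recurrence-free deaths, and nothing in the documents says so. The double deduction works in the plan's favour once removed. And 22–43% recurrence, the complement of the cited range, covers every value above.

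Much of this stands. A reader might infer that the control recurrences and the 80% power are definitely overstated, or that the arithmetic is wrong. The documents support neither: what the cited series (references 27 and 56–59) counted cannot be checked from them, and 35% is correct under one reading. A reader might also infer that the RFS counted transplants, leaving 15% recurrence and power near 54%. Nothing supports that either, and section 9.3.2 treats transplant as competing.

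What does not stand is that section 2.3 settles the matter. It defines this trial's endpoint, whereas the 65% is drawn from outside cohorts, and section 9.3.2 implies the opposite treatment of death. The 80% is also claimed for 47 per group, so power on 65 per arm does not rescue that statement unless the plan says that 65 is the basis.

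**Conclusion.** The concern holds in conditional form. The complement of a 65% RFS is used as a recurrence-only cumulative incidence beside 20% competing events, and the inputs agree only under a definition the plan never states. At 47 per arm with the plan's other inputs, power is 79% if that definition applies, about 76–78% for a recurrence-only Kaplan-Meier figure (about 31–32% vs 15–16% recurrence), and about 67–70% if deaths are counted and the source cohorts had 10% of them (about 23–25% vs 11–12%). Fewer deaths there give values in between. Against the reproduced 79%, the possible overstatement is 1 to about 12 points.

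All these figures rest on independent exponential times and on 42+15 months of follow-up. They isolate the effect of one input; they are not estimates of the trial's actual power.

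**What to change.** In section 9.3.1:

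- State whether the 57–78% figures count death and transplant. Give the control cumulative incidence of recurrence directly from the cited cohorts, or subtract those cohorts' own recurrence-free deaths from 1 − RFS.
- Replace the 35%-to-18% benchmark with the pair that matches that input and HR 0.45.
- Rerun and restate the power over the 12-month TTR window of section 2.3. Say whether 47 per arm is already net of competing events and drop-out, so that they are deducted once only.

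Make sections 2.3 and 9.3.2 agree on whether death is an RFS event. Do not simply write the 67–79% range into the protocol, because it inherits the 42+15-month follow-up and the possible double deduction.

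The cost is one recalculation, a check of the cited cohorts, and probably a less favourable stated power. Correcting this input does not itself require a design change; whether the restated power is acceptable is then for the sponsor to judge.
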